## 2. Study design

This study is a prospective, stepped-wedge cluster randomized trial to test the effectiveness of implementing a Clinical Decision Support (CDS) tool for prediction of septic shock in four Emergency Departments (ED) within a pediatric healthcare network. The site will be the unit of randomization. All ED providers at the site will receive the CDS intervention when their site receives the intervention. The outcomes will be measured at the patient level. There will be five, 10-week study periods and four sites. In the first period, no sites will receive the intervention. During each subsequent period, one site will crossover to receive the intervention.

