#### Minimal necessary sample size to fit the multivariable models

For the binary outcome of guideline-concordant care, the model for sensitivity analyses will have up to 9 degrees of freedom (intercept + 3 (4 sites) + 4 (five time periods) + 1 for treatment). Using the rule of tens, we must have at least 90 outcomes. In the worst case scenario, there will be no treatment effect and 25% of the sample should have the outcome. This yields a minimal needed sample of  $90/0.25 = 360$ . In a univariable test, assuming a minimal detectable difference of 0.25, The power attainable would be 99.9%.

In the event that the treatment and control groups are imbalanced for some covariates, and 5 parameters are added, approximately 140 outcomes will be necessary to fit the model adequately. Then the minimal sample size becomes:  $140/0.25 = 560$ . In a univariable test, assuming a minimal detectable difference of 0.25, The power attainable would be >99.9% under the expected sample size of 2054.

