## 6. Analyses

The primary hypothesis will test whether the proportion of patients receiving guideline-concordant septic shock care is greater in the intervention arm compared to the control arm. An odds ratio will be calculated to assess this, and will be considered significant if the 95% confidence interval does not contain 1.0.

Analyses will be conducted at the level of the patient encounter using the generalized linear model framework. The primary analysis will include an effect for intervention, and subsequent sensitivity analyses will include fixed effects for time and site to test for heterogeneity of effect. Up to five additional covariates will be included if they are imbalanced between the two arms of the trial. We will construct tables comparing the medians and proportions of clinically meaningful variables that might be expected to affect the association between the intervention and the outcome of guideline-concordant care. These potential covariates considered will include patient characteristics, provider type, arrival modality, triage level, and social determinants of health, including race, ethnicity, and insurance status. Standardized differences will be used to assess the magnitude of difference in covariates between arms. Anywhere that we find significant imbalance between arms, that variable will be included as a covariate.

Significance of effects will be assessed at the 5% level, with all tests structured as two sided hypotheses. SAS software version 9.4 (SAS Institute, Cary, NC) and R version 4 (R Foundation for Statistical Computing, Vienna, Austria) will be used for all data management and statistical analysis.

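### The sensitivity model is said to test heterogeneity of effect, but with a single treatment coefficient it can only adjust a common odds ratio for site and period

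*SAP*

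**What the plan says.** Section 6 describes two layers of analysis. For the first, "The primary analysis will include an effect for intervention". For the second, "subsequent sensitivity analyses will include fixed effects for time and site to test for heterogeneity of effect".

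The part of section 2.1 on the minimal sample size for the multivariable models specifies the second layer: "the model for sensitivity analyses will have up to 9 degrees of freedom", made up of "intercept + 3 (4 sites) + 4 (five time periods) + 1 for treatment". It continues: "Using the rule of tens, we must have at least 90 outcomes". The only extension is five parameters for imbalanced covariates, in which case "approximately 140 outcomes will be necessary to fit the model adequately".

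Section 2 gives the rollout over four sites and five periods: "In the first period, no sites will receive the intervention" and "During each subsequent period, one site will crossover to receive the intervention".

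The SAP contains no intervention-by-site or intervention-by-period term, no random treatment effect and no site-specific estimate. The subgroups in section 5.1 are defined by patient characteristics (predicted risk, race/ethnicity), not by site or period.

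**The concern.** A fixed effect for site lets the baseline rate of concordant care differ between emergency departments, and a fixed effect for period lets it drift over calendar time. Neither lets the effect of the tool differ. That needs a product of the intervention with site or period, or a random treatment effect. The purpose given in section 6 and the model listed in section 2.1 therefore do not match.

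Followed as written, the analysis gives one adjusted odds ratio and no information on how the effect varies. Under its stated label, that result could be read as evidence that the tool works equally well at all four sites. Significant site terms could be misread the other way, as differing effects, when they show only differing concordance rates.

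**Working it through.** **1. The SAP's own count (section 2.1).**
- Parameters: 1 + (4 − 1) + (5 − 1) + 1 = 9.
- Rule of tens at a 25% outcome rate: 9 × 10 / 0.25 = 360. With five covariates: 14 × 10 / 0.25 = 560.

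Both figures agree with the SAP. All 9 parameters are the intercept, site and period main effects, and one treatment effect, so none is left for variation in effect.

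**2. What the design can estimate.** Rank of the design matrix for 4 sites × 5 periods, one site crossing over at each of periods 2 to 5:

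| Model | Columns | Rank |
|---|---|---|
| Site + period + treatment | 9 | 9 |
| Plus intervention-by-site (3 terms) | 12 | 12 |
| Plus full intervention-by-period (4 terms) | 13 | 11 |

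The site interaction is fully estimable. Only 2 of the 4 period-interaction terms are, because no site is treated in period 1 and none is a control in period 5.

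**3. Size of the corrected model under the SAP's rule.** 12 × 10 / 0.25 = 480. With five covariates, 17 × 10 / 0.25 = 680. Both are below 2054. This shows that the model can be fitted, not that its test is well powered.

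**4. What the 9-parameter model would report.** Assumptions not in the SAP, used here and in steps 5 and 6: logistic model, independent patients, 2054 patients spread evenly over the periods, two-sided 5% level, and a 25% control rate at every site unless stated. Site volumes are either equal or 6:2:1:1 in any assignment to sites. Ranges run over all crossover orders.

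With site odds ratios of 1, 1, 3 and 3, fitting the listed model to expected data gives one common odds ratio:
- equal volumes: 1.61 to 1.99
- volumes 6:2:1:1: 1.31 to 2.42

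For this strong pattern, a 3-df interaction test would have about 98–99% power with equal volumes and 84–98% at 6:2:1:1.

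**5. Power under moderate heterogeneity.** Site odds ratios 1.5, 2, 2 and 3; 3-df Wald test, noncentral chi-square:

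| Control rates by site | Equal volumes | 6:2:1:1 |
|---|---|---|
| 25% at all sites | 30–50% | 15–59% |
| 15, 20, 30, 35% (any assignment) | 25–54% | 13–63% |

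**6. Precision of site-specific odds ratios, same effects.** The 95% limits lie a factor of exp(1.96 × SE) either side of the estimate.
- 25% everywhere, equal volumes: SE of the log odds ratio 0.24–0.31; factor exp(1.96 × 0.241) = 1.60 to exp(1.96 × 0.306) = 1.82.
- 25% everywhere, 6:2:1:1: SE up to 0.44; factor exp(1.96 × 0.443) = 2.38.
- Control rates of 15–35%: SE up to 0.35 with equal volumes, and up to 0.52 at 6:2:1:1, a factor of about 2.75.

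**The case against.** The strongest reply is that this is loose wording. The sentence speaks of sensitivity analyses and names only fixed effects, so the likely intent is to see whether the intervention effect holds once site and calendar time are allowed for. The listed model does that, and rewording one phrase would remove the contradiction. On this view the interaction test goes beyond the defect, and with 13–63% power against moderate heterogeneity it would often be inconclusive. The harm is also conjectural, since the SAP attaches no decision to this analysis and nowhere claims a uniform effect.

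Part of this stands. The wording may be the whole error, which is why the point is minor. But the SAP says that it will test heterogeneity, and the interaction is the way to do what it says. Against strong heterogeneity, as in the 1, 1, 3, 3 example, the test would have high power.

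A second objection is sound and should go with the fix. In a stepped wedge, each site's effect is estimated from its own before-and-after change relative to a shared period effect. If sites have different underlying trends, those differences enter the interaction terms and can look like heterogeneity. A significant result therefore needs as much caution as a non-significant one. The assumption of independent patients also makes the power and standard errors above optimistic.

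**Conclusion.** The concern holds. The model fixed in section 2.1 cannot test what section 6 says it will test. This follows from the parameter count alone and does not depend on any assumed volume, rate or effect size. The illustrative odds ratios, power and standard errors do depend on such assumptions, because the SAP gives no site volumes or site-specific rates.

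Severity is minor. The defect is confined to a supporting analysis. The SAP's 9 degrees of freedom, 360 and 560 are arithmetically correct for the model it lists.

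**What to change.** 1. In section 6, describe the fixed effects for site and period as adjustment of the common odds ratio for site differences and secular trend.
2. To address heterogeneity, add a joint 3-df intervention-by-site test to the sensitivity model, report site-specific odds ratios with 95% confidence intervals, and label this exploratory.
3. State that a non-significant test does not show a uniform effect, and that differing site trends can produce a significant one.
4. In section 2.1, give 12 degrees of freedom for the interaction model, with minimum sizes of 480, or 680 with five covariates.
5. Do not specify a full intervention-by-period interaction, since two of its four terms cannot be estimated.

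The cost is a few sentences, one extra model fit and a revised parameter count, with no new data. The drawback is low power against moderate heterogeneity and wide site-specific intervals, to a degree that depends on the actual site volumes and control rates.

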### **3. Aims and objectives**

The objective of this trial is to test whether implementing a CDS tool for prediction of septic shock in four Emergency Departments within the Children's Hospital Colorado network increases the proportion of children with suspected sepsis who receive guideline-concordant septic shock care, decreases the time to antibiotics, decreases the proportion of patients with septic shock, decreases the proportion of patients who experience mortality within 30 days of hospital arrival. An additional objective is to assess the balancing measure of whether the proportion of patients with suspected sepsis who receive intravenous antibiotics increases.

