##### Other hospital course and resource utilization outcomes

Organ dysfunction laboratories measured

Sepsis orderset used

Arrival to Antibiotic Administration

ED Disposition

24-Hour hypotension

Intravenous crystalloid fluid volume administered/kg in the first 24 hours

Vasoactive agent used during hospitalization

Positive pressure ventilation during hospitalization

Hospital Length of Stay

ICU within 24 hours

ICU Length of Stay

Proportion of all ED patients triggering the CDS

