## 5. Populations and subgroups to be analyzed

### 5.1 Subgroups

The primary analysis will be conducted in all patients meeting inclusion criteria. A subgroup analysis for the same outcomes will be conducted only in the subgroup of patients identified as high-risk by either the arrival or two-hour models. Assuming sufficient sample size, we will perform subgroup analyses in race/ethnicity groups, to assess whether the intervention differentially impacts socially constructed subgroups.

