### 6.2 Secondary outcomes (continuous – time to antibiotic)

The secondary hypothesis will test whether the time to antibiotics is shorter in the intervention arm compared to the control arm. A hazard ratio will be calculated to assess this, and considered significant if the 95% confidence interval does not contain 1.0. The following approach will be used.

Time will be measured beginning with admission to the ED and concluding with administration of antibiotics (an event) or discharge from the ED (censoring). Death is expected to be rare and will be treated as a censoring event. Analysis will use a Cox proportional hazard model with a fixed binary effect for treatment.

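### Below a properly singled-out primary outcome, the SAP tests at an unadjusted two-sided 5% with no order, adjustment or exploratory label, so false-positive error over the three secondary efficacy outcomes is about 10% to 14%

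*SAP*

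**What the plan says.** **Primary.** SAP section 4.1 names one primary outcome, and section 6 gives one primary hypothesis: "The primary hypothesis will test whether the proportion of patients receiving guideline-concordant septic shock care is greater in the intervention arm compared to the control" (the group without the tool). It is judged by whether the 95% CI for the odds ratio excludes 1.0.

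**Error rule.** Section 6 then states for the whole plan: "Significance of effects will be assessed at the 5% level, with all tests structured as two sided hypotheses".

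**Further efficacy effects.** Section 3 says the trial is to test whether the tool also "decreases the time to antibiotics, decreases the proportion of patients with septic shock, decreases the proportion of patients who experience mortality within 30 days", counted from arrival at hospital. Only time to antibiotics has its own decision rule, in section 6.2: "A hazard ratio will be calculated to assess this, and considered significant if the 95% confidence interval does not contain 1.0". That rule does not depend on the primary result. Section 2.1 also powers this outcome at 0.05.

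**Balancing measure.** Section 3 keeps intravenous antibiotic use apart from the efficacy effects: "An additional objective is to assess the balancing measure".

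**Other outcomes.** Section 4.2, on secondary outcomes, ends with a block of 12 items headed "Other hospital course and resource utilization outcomes".

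**Subgroups.** Section 5.1: "A subgroup analysis for the same outcomes will be conducted only in the subgroup of patients identified as high-risk" (flagged by at least one of the two prediction models). Race/ethnicity subgroups follow if the sample is large enough; their number is not given.

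No section adjusts for multiplicity, orders the secondary outcomes, or calls secondary, other or subgroup results exploratory.

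**The concern.** The SAP does more than leave multiplicity unmentioned. It states a significance rule that covers every test and exempts none, and it describes three secondary outcomes as effects the trial will test. Under that rule, if the primary result is null, a nominally significant result for antibiotic timing, shock, mortality or a subgroup may still be reported as significant.

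What is at stake is the standing of the claims below the primary. The 5% attached to each is the error rate of one test, not of the set from which a favourable result could be picked out afterwards. The primary conclusion is not affected.

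**Working it through.** **1. The plan's own figure.** The SAP states no family-wise error rate. The nearest stated figure is 80% power for time to antibiotics (mean log time 4.0 vs 3.8) at 0.05, in section 2.1.
- Patients with antibiotics per arm, assuming equal arms: 2054 × 0.79 / 2 = 811.
- Pooled SD from the SAP's 1.29 and 1.54: √[(1.29² + 1.54²)/2] = 1.42.
- Standard error: 1.4205 × √(2/811.33) = 0.0705.
- Power: Φ(0.2/0.0705 − 1.96) = Φ(2.836 − 1.960) = 80.9%.

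This reproduces the stated 80%. So the SAP's planning for this secondary outcome spends the full 5% on it alone.

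**2. Family-wise error for the three secondary efficacy outcomes.** Inputs: 3 outcomes (section 3), each at two-sided 5% (section 6), hence 2.5% in the direction of benefit. Correlation between the test statistics is not in the SAP, so a range is shown.
- Independent tests, either direction: 1 − 0.95³ = 14.3%.
- Independent tests, false benefit only: 1 − 0.975³ = 7.3%.
- Common correlation ρ, either direction: 1 − ∫ [Φ((1.96 − √ρ·u)/√(1−ρ)) − Φ((−1.96 − √ρ·u)/√(1−ρ))]³ φ(u) du. For benefit only, the second Φ term is dropped.

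| Correlation | Either direction | False benefit |
|---|---|---|
| 0 | 14.3% | 7.3% |
| 0.3 | 13.6% | 6.8% |
| 0.5 | 12.5% | 6.3% |
| 0.8 | 9.8% | 4.9% |
| Nominal, one test | 5% | 2.5% |

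Inflation is about two- to three-fold in both columns, at every correlation tried.

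**3. Larger families (illustration only).** If each of the 12 other outcomes were also tested and read as a claim, there would be 3 + 12 = 15 tests. The rate would be 53.7% (independent) down to about 20% (correlation 0.8) in either direction, and 31.6% down to about 10% for a false benefit. The SAP does not say that each of the 12 is tested, so these are not rates of the plan. No rate is given for the race/ethnicity groups because neither their number nor their outcomes are fixed.

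**4. With control.** Bonferroni over three tests at 0.05/3 = 0.0167, independent: 1 − (1 − 0.0167)³ = 4.9% in either direction; 1 − (1 − 0.0083)³ = 2.5% for a false benefit. Holm or a fixed order also holds the rate at or below 5%.

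**5. Cost in power for time to antibiotics.** At Holm's strictest step (0.0167, critical value 2.394), power for 4.0 vs 3.8 is Φ(2.836 − 2.394) = 67%. For the planned 4.0 vs 3.3 it stays above 99.9%, since 0.7/0.0705 = 9.9. In a fixed order with this outcome placed directly after the primary, its own test stays at 5% and 80.9%, once the primary has succeeded.

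**The case against.** The strongest reply is that the SAP already has tiers: one primary hypothesis, one secondary hypothesis stated in the singular with its own rule, and a block of other outcomes. Only the primary and time to antibiotics are powered. On this view section 6 gives a general convention, and readers know that secondary results are supportive.

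Much of this stands. Three stronger readings that a reader might infer are not supported:

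- **That the trial has no hierarchy, or that its primary error rate is inflated.** One primary is named with its own rule. What is missing is an order, adjustment or label below it.
- **That all 12 other outcomes are formally tested.** The SAP does not say so. Some, such as ED disposition or the proportion of ED patients who trigger the tool, have no clear direction of benefit. Some overlap with the secondary outcomes, so independence would overstate the rate.
- **That a false claim of benefit is likely.** For the three efficacy outcomes it is about 5% to 7%. Higher figures need many more tests, all read as claims, or an assumed number of race/ethnicity groups. Section 5.1 makes those analyses conditional, and their purpose is to see whether the effect differs between groups.

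The reply does not remove the core. Section 6 does not exempt anything from its 5% rule, section 3 presents the three effects as things to be tested, section 6.2 lets one be declared significant whatever the primary shows, and nothing is labelled supportive or exploratory.

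**Conclusion.** The point holds for results below the primary. For the three secondary efficacy outcomes, the family-wise false-positive rate under no effect is about 10% to 14% in either direction, or about 5% to 7% for a false benefit against a nominal 2.5%. The range reflects an assumed common correlation from 0.8 to 0.

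The figures also assume that each single test holds its nominal level. Whether the intervention-only models of sections 6 and 6.2 do so in a four-site stepped wedge is a separate question that multiplicity control would not answer. Rates for the 12 other outcomes and the race/ethnicity groups depend on choices the SAP does not fix, so none is claimed.

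This is a matter of what may be claimed from secondary and subgroup results. It should be settled before analysis, but it does not threaten the primary conclusion.

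**What to change.** In section 6, keep the two-sided 5% rule for the primary outcome and replace the blanket rule for everything else:

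1. Allow confirmatory claims for time to antibiotics, septic shock and 30-day mortality only if the primary is significant. Control error across the three at two-sided 5% by Holm or by an order fixed in advance. Labelling all three supportive, with no confirmatory claim, would close the gap equally well.
2. Make the section 6.2 decision rule subject to item 1.
3. Report the intravenous antibiotic balancing measure outside this family, as an estimate with a 95% CI, so that a signal of overuse is not suppressed.
4. Label the 12 other outcomes in section 4.2 and all section 5.1 subgroup analyses exploratory, with estimates and 95% CIs and no significance claims.

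**Cost.** SAP wording only, with no new data. The primary's alpha, power and sample size do not change. A secondary outcome may not be claimable as confirmed if the primary or an earlier step is not significant, and Holm lowers power for small secondary effects. The choice between Holm and a fixed order, and the ranking in a fixed order, are for the sponsor to make and record before the data are analysed.

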### 6.2 Secondary outcomes (continuous – time to antibiotic)

The secondary hypothesis will test whether the time to antibiotics is shorter in the intervention arm compared to the control arm. A hazard ratio will be calculated to assess this, and considered significant if the 95% confidence interval does not contain 1.0. The following approach will be used.

Time will be measured beginning with admission to the ED and concluding with administration of antibiotics (an event) or discharge from the ED (censoring). Death is expected to be rare and will be treated as a censoring event. Analysis will use a Cox proportional hazard model with a fixed binary effect for treatment.

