### 2.1 Sample size calculation

The unit of analysis for this study is ED patients with suspected sepsis. The necessary enrollment size was used to calculate the study period necessary to achieve power, based on historic volume trends. The main calculations were done using the `pwr` package for R.

During the study period, we expect 2054 patients to be identified and exposed to decision support (CDS). With current care patterns, we would expect 25% (514) to receive guideline-

concordant septic shock care prior to shock occurring. In the literature, use of pediatric sepsis quality interventions has increased rates of concordant early care of shock to 50% (1027). With an estimated effect of the alert of increasing rates of concordant care from 25% to 50%, using a significance of 0.05, we anticipate >90% power to detect this difference. We will have 80% power to detect an increase of 6%.

For the outcome of time to receipt of antibiotic, we expect that 79% of patients will receive antibiotics. Among those who do receive antibiotics, with current care patterns, in pilot data we have observed a mean time to antibiotics of 55 minutes, or a mean log time of 4.0 (SD 1.29). In published pediatric sepsis literature, the use of pediatric sepsis quality interventions has decreased the log time to antibiotic to 3.3 (SD 1.54). Using a significance of 0.05, we anticipate >90% power to detect a difference in this outcome. We have 80% power to detect a smaller difference of 4.0 vs 3.8 (55 to 45 minutes). Even under conditions of very slow accrual where half of the hypothesised sample is realized, we would have 80% power to detect a difference of 4.0 vs 3.72 (55 to 41 minutes).

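### The Cox hazard ratio in SAP 6.2 mixes how fast children are treated with how many are treated, so it cannot alone show a shorter time to antibiotics, and the 80% power in 2.1 belongs to a different comparison

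*SAP*

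**What the plan says.** Section 6.2 sets the hypothesis: "The secondary hypothesis will test whether the time to antibiotics is shorter in the intervention arm compared to the control arm". The test is a Cox model with a binary treatment term. Antibiotic administration is the event, and ED discharge or death is censoring. The conclusion follows if the 95% confidence interval of the hazard ratio excludes 1.0. No set restricted to treated children is defined for this analysis, and section 5.1 takes all children meeting the inclusion criteria for the primary analysis.

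Section 2.1 sizes the outcome differently: "we expect that 79% of patients will receive antibiotics. Among those who do receive antibiotics", the pilot data gave a "mean time to antibiotics of 55 minutes, or a mean log time of 4.0 (SD 1.29"). The calculation is therefore a comparison of mean log time within recipients.

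Section 3 adds a balancing measure: "whether the proportion of patients with suspected sepsis who receive intravenous antibiotics increases". Section 4.2 lists the number given IV antibiotics as an outcome of its own. Nothing in 6.2 says how the hazard ratio is to be read if that number differs between arms.

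**The concern.** An untreated child stays in the Cox risk set until discharge and never has the event. If the decision support leads clinicians to treat more children, each no sooner than before, the hazard of antibiotic receipt rises and the ratio moves above 1. Under 6.2 that is reported as a shorter time. If clinicians instead treat fewer children but treat those faster, the two effects cancel and the gain is lost.

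At stake is what the trial may say on its first-listed secondary outcome. One change in behaviour, treating more children, would move both this outcome and the balancing measure, and the SAP gives no rule for telling it apart from faster treatment. The power statement in 2.1 also does not describe the test in 6.2.

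**Working it through.** **1. Reproduce the plan's own figure.** Inputs from 2.1: 2054 children, read as the total of both arms; 79% treated; log time 4.0 (SD 1.29) against a literature SD of 1.54; two-sided 5%. Equal arms are assumed (10 control and 10 intervention site-periods).
- Recipients per arm: 2054/2 × 0.79 = 811.
- Pooled SD: √((1.29² + 1.54²)/2) = 1.42.
- Power for 4.0 v 3.8 is Φ(0.2/(1.42·√(2/811)) − 1.96) = 0.81, against the stated 80%.
- At half accrual, 4.0 v 3.72 gives 0.80, also as stated.

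Reading 2054 as per arm would give 0.98. The 80% is therefore a two-sample comparison of log time among recipients. With SD 1.29 in both arms the same comparison has 0.878.

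**2. Direction of the effect, without assuming an ED stay.** Let p be the share treated, f and S the density and survivor function of recipients' times (the same in both arms), and G(t) the proportion of untreated children still in the ED. The hazard in an arm is

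h(t) = p·f(t) / [p·S(t) + (1 − p)·G(t)].

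The ratio of intervention (p₁) to control (p₀) is

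(p₁/p₀) × [p₀S + (1 − p₀)G] / [p₁S + (1 − p₁)G].

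Cross-multiplying, this exceeds 1 exactly when p₁ > p₀, at every time when G > 0. It starts at p₁/p₀ = 0.84/0.79 = 1.06 and varies over time, so hazards are not proportional. Its size depends on G, which the SAP does not give.

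**3. Size, by simulation of the 6.2 model.** There were 1027 children per arm, lognormal times among recipients (4.0, SD 1.29 in both arms unless stated), and control share 79%. Assumed: untreated children are censored at a lognormal ED stay with median 180 to 480 min and log SD 0.5; children newly treated have the same times as others; no clustering or period effects.

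| Intervention share | Recipients' log time | Hazard ratio | Result under 6.2 |
|---|---|---|---|
| 79% | 4.0 | 1.00 | shorter in 2–4% |
| 82% | 4.0 | 1.06–1.08 | shorter in about 19–33% |
| 84% | 4.0 | 1.10–1.13 | shorter in about 47–71% |
| 74% | 4.0 | 0.89–0.91 | slower in about half to two-thirds |
| 74% | 3.8 | 0.95–0.99 | true gain found in about 2% or fewer |
| 79% | 3.8 | above 1 | true gain found in about 29–45% |

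The first two rows also cover censoring later than every event. If 90% are treated and recipients are slower (4.2), the hazard ratio is still 1.12 to 1.24 and shorter is declared in 66 to 99% of trials (run with a median stay of 240 min and with late censoring only).

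**4. The recipient comparison in the same data.** With timing unchanged, it declares faster treatment in about 2 to 4% of runs, against a nominal 2.5%. In the 74% and 3.8 scenario it finds the gain in 86 to 89%.

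**5. Power.** The last row of the table, 29 to 45%, is the Cox test's power for the difference to which 2.1 attaches 80%. Like for like (SD 1.29 in both arms), the recipient comparison has 88%.

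**The case against.** A Cox model over all included children is a legitimate analysis. Section 4.2 calls this a time-to-event outcome, and keeping untreated children in the risk set preserves the comparison by randomised exposure; restricting to recipients does not. If more children are treated with unchanged timing, the proportion treated by any given time is higher, so for the whole population the null is false. This stands: the percentages above are wrong conclusions about speed, not type I error for the whole-population hazard. The ratio may stay, but it needs a label that says what it measures.

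A reader might infer that the plan would report antibiotic overuse, a harm, as a benefit. The SAP does not support that. It says balancing measure and never harm. The introduction mentions overuse to explain why the models were confined to children in whom sepsis was already suspected, and extra treatment in that group is not necessarily overuse. The share treated is also a listed outcome, so a rise would be visible. What is missing is any link between it and the decision in 6.2.

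The sizes rest on an intervention-arm share and an ED stay that the SAP does not state, on newly treated children having the same timing as others, and on independence within sites. They illustrate the problem and do not forecast error rates. The simulations also use the log times of 2.1 without settling whether they run from sepsis recognition (4.2) or ED admission (6.2). Those two starting points need reconciling, but the point here arises with either clock.

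**Conclusion.** The point holds as one of interpretation and of power. The hazard ratio in 6.2 combines speed among recipients with the share treated. A difference in share alone moves it in a known direction, whatever the ED stay. Under the stated assumptions, five percentage points more children treated (79% to 84%) is enough for shorter time to be declared in roughly 47 to 71% of trials with no change in speed. Five points fewer conceals a real gain from 4.0 to 3.8. Separately, the 80% power in 2.1 is for log time among recipients; for the same difference with equal shares, the Cox test has about 29 to 45%.

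The documents do not show that the Cox model is invalid, that a rise in treatment would be harmful, or that these frequencies should be expected in this trial. The outcome is secondary, and the primary outcome has its own 60-minute criterion.

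**What to change.** In 6.2, label the hazard ratio as the rate of first IV antibiotic among all children with suspected sepsis, and state that a shorter time will not be concluded from it alone. In the same table report (a) the share treated in each arm and (b) the log-time comparison among recipients that 2.1 sized, marked as supportive because recipients are a subset formed after exposure. State that the three are read together. In 2.1, say that the 80% power applies to the recipient log-time comparison and not to the Cox test.

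A formal rule requiring both a hazard ratio above 1 and faster recipients is tempting but should not be adopted. It cannot recover a gain hidden by a lower share treated: at 74% and 3.8 it succeeds in 0.1 to 1.5% of runs, as does the Cox test alone. It can also be misled by who is newly treated: if the added 5% of children have a mean log time of 3.0 (assumed) and nobody else is faster, it still declares shorter time in 14 to 16%.

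The cost is SAP wording, one extra model, and a less simple claim for this secondary outcome.
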